1.2 Objectives

The study objectives are 1) to test the impact of the NOHARM intervention on pain and function 3 months following surgery, 2) test the impact of the NOHARM intervention on anxiety and opioid use during the 3 months following surgery.

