4.2 Secondary Objectives

To test the impact of a bundled NOHARM Healing after Surgery Guide + clinical decision support intervention embedded within an EHR on anxiety and opioid use during the 3 months following surgery.

5 **BACKGROUND AND RATIONALE**

5.1 **Background on Condition, Disease, or Other Primary Study Focus**

[figure not shown]
Prescriptions for narcotic pain relief after surgery result in unintended prolonged opioid use for hundreds of thousands of Americans.^{1,2} That trend fuels an excess supply of opioids that can lead to dependence, addiction, diversion, and overdoses on a national scale.³⁻¹⁰ Non-pharmacological pain care (NPPC) is effective and recommended by guidelines for perioperative pain while offering a more favorable risk-to-benefit ratio.¹¹⁻¹⁴ Additionally, patient and clinician decision support interventions are effective in encouraging patient-centered and guideline-concordant care in many other areas of medicine and hold great promise for promoting and facilitating post-operative non-pharmacologic pain management.^{15,16}

5.2 **Study Rationale**

Nonpharmacological pain care is rarely used as first or second-line therapy after surgery, despite guidelines to the contrary.^{17,18} NPPC offers a more favorable risk-to-benefit ratio than opioid medications which may play a critical role in acute post-operative management but should be tapered in favor of safer and more sustainable analgesic options as patients transition home and gradually resume their life roles. Additionally, patient and clinician support interventions have not been tested pragmatically as a bundle in everyday postoperative care as a means of facilitating the uptake of non-pharmacological pain management strategies in the perioperative setting and in the post-acute recovery timeframe. This study will address this knowledge gap and test the impact of utilizing patient and clinician decision support tools to inform patients and facilitate their preference for non-pharmacological pain management modalities.

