6 STUDY DESIGN

This study will utilize a cluster randomized stepped wedge design. Clusters are defined at the level of care teams and qualifying surgical procedures, and have been randomized to one of five different tranches to implement the intervention at staggered intervals (one new cluster each wave, see diagram below).

The primary outcome of the study is a composite of patient reported pain and function at three months post-surgery. This will enable us to determine the effectiveness of a bundled NOHARM Healing after Surgery Guide + clinical decision support for promoting non-pharmacological pain management strategies to patients undergoing qualifying surgeries, which may also ultimately curb overall patient demand for opioid prescriptions in post-acute post-surgical rehab while optimizing functional recovery. Thus, our secondary outcome(s) is opioid use at the 3 month point post-operatively. This will enable us to understand the impact of our EHR-embedded decision support intervention in an era where opioid prescribing is already being constrained.

All patients receiving common, pre-defined procedures within 7 surgical practice areas at 6 Mayo Clinic locations will receive the study intervention if their surgery date coincides with the stepped wedge implementation schedule. Study locations include Mayo Clinic Rochester, Mayo Clinic Florida, and Mayo Clinic Arizona, as well as three Mayo Clinic Health System sites (Mankato, MN; La Crosse, WI; and Eau Claire, WI). Surgical practice areas will include orthopedic surgery, colorectal surgery, gyn surgery, obstetrics, pulmonary/thoracic surgery, liver and kidney transplant, and cardiac surgery. Due to variable combining of post-op unit care areas, practice size, and related considerations we have formed 22 clusters that will be randomized across 5 tranches.

Enrollment in the intervention arm of the trial will extend from March 2021 to approximately August 2023. Participating practices will be enrolled in the study from the point in time the intervention is implemented in their practice and continuing through the end of the study.

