3. Opioid use will be measured using 4 outcomes:

- a. Hospital-based consumption, daily oral morphine equivalents (OMEs). This is a continuous measure for each day of hospitalization; we will assume that this depends in part on the day post surgery, D_{ij} and model

$$Y_{ij} = \beta_0 + \beta_I I_{ij} + \beta_D D_{ij} + \beta_T T + \mathbf{B}_X \mathbf{X}_{ij} + \mathbf{B}_Z \mathbf{Z}_j + u_j + e_{ij} \quad (3)$$

For this model we will consider D_{ij} as first continuous and then as categorical.

- b. Discharge and post-discharge prescriptions, daily oral morphine equivalents (OMEs). For this outcome, we will use a model analogous to (3), where D_{ij} is replaced by number of days post discharge.
- c. Number of post-discharge prescriptions. These are counts for the 3 month period following surgery. The impact of the intervention will be assessed using a model similar to (2) but with a Poisson link function:

$$\ln(E(Y_{ij})) \sim \beta_0 + \beta_I I_{ij} + \beta_T T + \mathbf{B}_X \mathbf{X}_{ij} + \mathbf{B}_Z \mathbf{Z}_j + u_j + e_{ij} \quad (4)$$

$$Y_{ij} \sim \text{Poisson}(\mu)$$

We will assess the distribution first using an empty model, and potentially adopt a zero inflated Poisson, negative binomial, or zero inflated negative binomial according to the corresponding AIC values.

- d. Daily use of opioids; this is binary outcome collected one time, at 3 months post-surgery. To assess the impact of the intervention we will use a model similar to (4) but with a logit link:

$$\text{logit}(Y_{ij}) \sim \beta_0 + \beta_1 I_{ij} + \beta_2 T + \mathbf{B}_X \mathbf{X}_{ij} + \mathbf{B}_Z \mathbf{Z}_j + u_j + e_{ij} \quad (5)$$

For a-d we can again test $\beta_1 = 0$ we can assess whether the intervention is associated with changes in the corresponding measure.

4. Healthcare utilization

- a. Hospitalizations
- b. ER visits
- c. Calls to surgical practice

All three of these are count outcomes, and so we will assess the impact of the intervention using a model similar to (4) above. As with (4), we will compare model specifications using an empty model first to determine the best count family (Poisson, negative binomial, zero inflated or not) using AIC, then apply that in the final model.

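### Opioid outcomes 3a and 3b are divided at discharge, and no outcome gives the opioid amount per patient over the 3 months named in the objective

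*Combined protocol and SAP*

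**What the plan says.** The objective in section 1.2 is to "test the impact of the NOHARM intervention on anxiety and opioid use during the 3 months following surgery", and section 4.2 repeats that window. Section 6 states a different target: "our secondary outcome(s) is opioid use at the 3 month point post-operatively".

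Section 12.5 item 3 lists four opioid outcomes without ranking them or saying which one answers the objective:

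- **3a:** daily OME consumed in hospital. "This is a continuous measure for each day of hospitalization; we will assume that this depends in part on the day post surgery". Day post surgery, D, is a covariate: "For this model we will consider D_{ij} as first continuous and then as categorical".
- **3b:** "Discharge and post-discharge prescriptions, daily oral morphine equivalents (OMEs"), in a model like (3) "where D_{ij} is replaced by number of days post discharge".
- **3c:** the number of post-discharge prescriptions, counted over the 3 months after surgery.
- **3d:** daily opioid use, yes or no, asked once at 3 months.

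The models carry a random intercept for cluster and a term for calendar time T, but no patient-level random effect. Length of stay is neither an outcome nor a covariate. Section 12.4.2 concedes that outpatient prescriptions are an inaccurate measure of consumption. Section 13.1.2 notes that some discharge prescriptions are written before the procedure.

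**The concern.** Discharge day is determined after exposure. The intervention works on pain management during the stay and at discharge (section 9.2.2, Touchpoints 3 and 4), so it could plausibly change when patients leave.

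If patients with low opioid need go home sooner in the intervention phase, the later hospital days in that phase hold a heavier-using mix than the same days under control. Conditioning on D compares like days, but not like patients. The opioid those patients take after leaving passes from 3a to 3b, where the clock restarts.

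The effect on opioid amount could then be understated or given the wrong sign in 3a, raised in 3b for reasons unrelated to use, and captured whole in neither. No planned result would answer the secondary objective as an amount.

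**Working it through.** **Inputs.** The plan has no figure to reproduce: it gives no effect size, SD or power for any opioid outcome, and no length of stay by group. The only stay figure is the assumed median of 3 days in Appendix A, used there to count clinicians. All OME levels and discharge patterns below are assumptions.

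**1. Coverage of the objective.**

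| Outcome | Quantity | Window |
|---|---|---|
| 3a | administered OME, per day | surgery to discharge |
| 3b | prescribed OME, per day | discharge to 3 months, clock from discharge |
| 3c | number of prescriptions | 3 months, no amount |
| 3d | yes/no | one time point |

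None is an amount from surgery to 3 months.

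**2. 3a with D in the model.** Assume half the patients use 20 OME/day and half 60. Controls stay 3 days. In the intervention phase a fraction f of low users leave after 2 days. With D categorical and no other covariates, the estimate is Σw_dΔ_d / Σw_d, where Δ_d is the difference in means on day d, w_d = n0·n1/(n0+n1), and n0 and n1 are the control and intervention numbers still in hospital, each relative to one full group.

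- Days 1 and 2: w = 0.5 each; Δ = 0 with no effect, or 38 - 40 = -2 with a true 5% cut.
- Day 3: n1 = 1 - f/2; the intervention mean is (40 - 10f)/n1, times 0.95 under the cut; w = n1/(1 + n1).

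| f | True cut | n1 | Day-3 mean | Δ3 | w3 | Estimate |
|---|---|---|---|---|---|---|
| 0.2 | none | 0.9 | 42.22 | +2.22 | 0.474 | +0.71 |
| 0.4 | none | 0.8 | 45.00 | +5.00 | 0.444 | +1.54 |
| 1.0 | none | 0.5 | 60.00 | +20.00 | 0.333 | +5.00 |
| 0.4 | 5% | 0.8 | 42.75 | +2.75 | 0.444 | -0.54 |
| 1.0 | 5% | 0.5 | 57.00 | +17.00 | 0.333 | +2.75 |

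For example, the last row is (-2 + 17 × 0.333)/1.333 = +2.75, although use over the three days falls from 120 to 114 OME per patient. With D linear, the third row gives +4.71 instead of +5.00.

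Under the 5% cut, w3Δ3 = (-2 + 10.5f)/(2 - 0.5f). The estimate is zero when this equals 2, so -2 + 10.5f = 4 - f and f = 6/11.5 = 0.52. In this example the sign turns only when just over half of low users leave early.

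**3. How far this depends on selection (no true effect).**

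- Equal fractions of both types leave early: 0.0.
- 40% of low and 20% of high users leave early: n1 = 0.7, mean 30/0.7 = 42.86, Δ3 = 2.86, w3 = 0.412; estimate 2.86 × 0.412/1.412 = +0.8.
- Types at 30 and 50 OME, 40% of low users leave early: mean 34/0.8 = 42.5; estimate 2.5 × 0.444/1.444 = +0.8.

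**4. With cluster and calendar time.** A stepped-wedge simulation used 22 clusters, 6 periods, 5 waves, 400 patients per cluster-period and 12 replicates. Daily OME declined exponentially (rate 0.3, patient log-SD 0.6), and the mean stay of 4 days was shortened by about 1. Estimates for 3a under a true 5% cut:

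| Discharge pattern | Linear D | Categorical D | Stay unchanged |
|---|---|---|---|
| unrelated to need | -1.9 | -2.1 | -1.8 |
| low users leave first | +0.7 | +0.8 | -2.0 |
| only low users leave earlier | +2.7 | +2.3 | -2.1 |

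With a true 10% cut, the last two patterns gave -1.4/-1.3 and +0.2/-0.1, against about -4.3 with stay unchanged. A linear calendar trend in stay with no intervention effect gave -0.3 to 0.0.

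**5. 3b on days since discharge.** Let need be 60·exp(-0.4t) on day t after surgery. The first day after a 4-day stay (days 0 to 3) is t = 4: 12.1 OME. After a 3-day stay it is t = 3: 18.1, or 17.2 with a 5% cut. The same post-discharge day therefore shows a rise although need on every post-surgery day fell. In the simulation 3b rose by 1.1 to 3.2 in every shorter-stay scenario despite a 5% or 10% cut. This takes prescribing to track need, but does not require low users to leave first.

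**6. A window fixed from surgery.** In the simulation, total use over days 0 to 13 gave -11 to -12 OME per patient for the 5% cut whether or not stay changed. That total is actual use, which the EHR does not hold. With administered plus prescribed OME, the f = 1, no-cut example lowers the in-hospital part from 120 to 110. If the discharge prescription is unchanged, the total falls by 10 OME with no change in consumption.

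**The case against.** The strongest reply is that the bias in 3a rests on an effect the documents never state: a stay shortened selectively in low users. That stands. With equal shortening the bias is nil, with partial selection it is modest, and the +2.75 needs every low user and no high user to leave early. The small example also omits surgery type, which section 12.5 puts in every model and which may absorb part of the link between need and stay. The simulation adds cluster and calendar time but not surgery type.

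Three stronger readings are tempting and are not supported:

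- **That 3a will rise while opioid use falls.** This takes marked selection. In the rows with no true cut, only opioid given in hospital falls; use is unchanged.
- **That any drift in stay over time biases 3a.** T is in the model and absorbs a linear drift. Only drift not captured by T would matter.
- **That nothing is measured over the 3 months.** 3c is a 3-month count, and the 3b data run to the 3-month point. What is missing is an amount from surgery.

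It is also fair to say that separate in-hospital, prescribed and self-reported measures are a defensible set of secondary outcomes, and that a combined total has its own bias (step 6). Both are reasons to add a total beside the components, not to demote all of them. They do not explain which result answers the objective, or why section 6 names a different window.

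**Conclusion.** The point holds in limited form. From the text alone: 3a and 3b are divided at a post-exposure event, no outcome gives an OME amount per patient from surgery to 3 months, and section 6 disagrees with sections 1.2 and 4.2 on the window.

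Conditionally: if stay shortens mainly in low-need patients, adjustment for D does not protect 3a. In the assumed example a true -2.0 OME/day is reported as -0.5 at 40% early departure and +2.75 at 100%. If prescribing tracks need, earlier discharge alone can raise 3b. The sizes are illustrative and the direction depends on the discharge mechanism. This affects a secondary objective and is inexpensive to correct, so the plan should be changed.

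**What to change.** 1. Name, as the analysis for the secondary opioid objective, one OME total per patient over a window fixed from surgery: administered in hospital plus prescribed at or after discharge, day 0 to day 90, including discharge orders written before surgery. Use a model like (2) with a skewed or two-part form.
2. Put 3b on days since surgery, or replace it with total prescribed OME to day 90.
3. Keep 3a, 3c and 3d. Report the administered part, the prescribed part and length of stay by group beside the total.
4. Reconcile section 6 with sections 1.2 and 4.2.
5. Do not substitute a short early in-hospital window, such as 48 hours, unless nearly all patients are still admitted throughout it; otherwise discharge truncates it too.

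**Cost:** SAP wording and one derived variable; the components are already extracted (sections 12.4.2 and 13.1.2). **Downside:** the total mixes administered and prescribed OME, is not consumption, and can fall slightly when stay shortens with an unchanged prescription. It should be labelled accordingly and read with its parts.

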12.5 Data Analyses

Because patients are randomized in clusters, all statistical methods will account for potential correlation of measures within clusters. Such methods include cluster adjusted standard errors for t-tests and χ^2 -tests, and mixed effects models. Patient characteristics will be summarized by intervention status, and tested for difference between intervention groups; any factors which are imbalanced will be accounted for in the main analyses. Factors assessed for balance and potential inclusion in pre-specified analyses are those listed in Section 13.1.1 and all baseline measures listed in 13.1.2.

The primary and secondary outcomes will be compared between intervention groups using mixed effects generalized linear models. Each model will include an indicator for intervention group; a random intercept for cluster; cluster level factors that were used to constrain randomization; calendar time; surgery type; and any patient factors that were imbalanced across groups.

The model details for each outcome are as follows:

1. PROMIS CATs (anxiety (1°), physical function (1°), pain (1°)). These are continuous measures, collected at two time points, pre-operative and 3 months post-operative. To assess the impact of the intervention on these we will estimate three separate models. If Y_{ijt} is the measure at time $t=1,2$ of the i th patient treated by the j th cluster, then we will estimate

$$Y_{ij2} = \beta_0 + \beta_I I_{ij} + \beta_B Y_{ijo} + \beta_T T + \mathbf{B}_X \mathbf{X}_{ij} + \mathbf{B}_Z \mathbf{Z}_j + u_j + e_{ij} \quad (1)$$

where I_{ij} indicates the intervention status, T is calendar time, $u_j \sim N(0, \tau^2)$ is a cluster level random effect, X_{ij} is a vector of patient characteristics, including surgery type, Z_j is a vector of cluster characteristics used for randomization, and e_{ij} is a residual error. By testing $\beta_I = 0$ we can assess whether the intervention is associated with changes in the corresponding measure.

2. NPPC use. This is collected as a binary value for each of 14 modalities, collected at one time point, 3 months post-operative. We will sum these to create a score, and use a model similar to (1) but without a baseline value Y_{ij0} :

$$Y_{ij} = \beta_0 + \beta_I I_{ij} + \beta_T T + \mathbf{B}_X \mathbf{X}_{ij} + \mathbf{B}_Z \mathbf{Z}_j + u_j + e_{ij} \quad (2)$$

Again by testing $\beta_I = 0$ we can assess whether the intervention is associated with changes in the corresponding measure.

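### Daily opioid dose (items 3a and 3b) is tested with an additive linear model whose model-based standard error would be too small if opioid trends in mg differ between practices

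*Combined protocol and SAP*

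**What the plan says.** Section 12.5 opens with a general rule: "The primary and secondary outcomes will be compared between intervention groups using mixed effects generalized linear models". Each model contains an intervention indicator and "a random intercept for cluster; cluster level factors that were used to constrain randomization; calendar time; surgery type", plus any patient factors found to be imbalanced.

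Item 3a is headed "Hospital-based consumption, daily oral morphine equivalents (OMEs"). It says of the outcome: "This is a continuous measure for each day of hospitalization; we will assume that this depends in part on the day post surgery". Model (3) follows:

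Y = β0 + βI·I + βD·D + βT·T + BX·X + BZ·Z + u_j + e_ij

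The response is untransformed OME, and there is one intervention coefficient and one calendar-time coefficient. A distribution is written only for u_j (normal). Under model (1) the plan says no more of the error than "e_{ij} is a residual error". A single residual variance is therefore implied, not stated.

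Item 3b covers OME prescribed at and after discharge: "For this outcome, we will use a model analogous to (3"), with day after surgery replaced by days since discharge.

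For the number of prescriptions (3c) the plan adds "We will assess the distribution first using an empty model", with a choice of count family by AIC. Item 4 repeats this for utilisation counts. No such step is given for 3a or 3b, and no term lets calendar time differ by practice or surgery type.

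Section 6 lists the seven surgical areas, from obstetrics to transplant and cardiac surgery. It describes the setting as one "in an era where opioid prescribing is already being constrained".

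**The concern.** A random intercept and a surgery-type main effect absorb differences in opioid level between practices. They do not absorb differences in slope. If opioid use falls by a similar percentage everywhere, a practice with high use falls by more mg than one with low use. A common time term, linear or categorical, captures only the average mg fall. What is left is shared by all patients in a cluster and, once clusters are allocated to waves, is correlated with intervention status. The model treats that leftover as independent patient noise, so its standard error is too small.

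Opioid use is part of the secondary objective, and 3a and 3b are its dose-based tests. At stake are their error rate and, separately, their power if the intervention acts proportionally.

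**Working it through.** **The plan's own figure.** There is none for OME. The only power figure (section 12.2, 0.048 to 0.055 SD) concerns the pain score, so there is nothing to reproduce here.

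**Inputs from the documents.** 22 clusters, 5 waves (6 periods with baseline), 114,000 patients, and about 30 months of intervention enrolment (section 6). Section 12.2.1 constrains randomisation on site, volume, procedure group and number of teams, not on opioid level.

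**Assumed inputs.** One value per patient; practice means centred on 30 mg/day with log-SD 0.4 to 0.7; within-practice CV 1.3; a uniform fall of 10 to 30% over the roll-out. Analyses of 57,000 (half the planned number) and 114,000 patients.

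**Step 1: the term the model lacks.** Let practice j have mean m_j and let use fall by a fraction f, with t running from 0 to 1. The mean is m_j(1 − f·t). A common time term removes the average, m̄·f·t, and leaves −(m_j − m̄)·f·t. At log-SD 0.7, practices one log-SD above and below the centre have means 30·e^0.7 = 60.4 and 30·e^−0.7 = 14.9 mg/day. A 20% fall is 12.1 mg/day in one and 3.0 in the other. At log-SD 0.4 the means are 44.8 and 20.1, and the falls are 9.0 and 4.0.

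**Step 2: type I error, no true effect, nominal 5%.** 2,000 simulated trials per cell with period fixed effects, which is more generous than the plan's single T. Entries are the linear model with pooled residual variance / a log-scale model, in %.

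| Patients | log-SD | 20% fall | 30% fall |
|---|---|---|---|
| 57,000 | 0.4 | 6.5 / 6.4 | 7.6 / 4.8 |
| 57,000 | 0.7 | 8.6 / 5.3 | 13.9 / 5.6 |
| 114,000 | 0.4 | 6.8 / 4.9 | 11.7 / 6.1 |
| 114,000 | 0.7 | 12.1 / 5.4 | 19.5 / 5.1 |

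A repeat with 800 trials per cell gave 6-13% at 57,000 and 7-23% at 114,000 for the linear model. With a 10% fall the rates were 5-7% over the two runs.

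**Step 3: sensitivity to the assumptions.** A second set-up used gamma data with within-practice CV 1.0 and a random-intercept model, at 114,000 patients. A 20% fall gave about 7%, 10-12% and 15% at between-practice CV 0.3, 0.5 and 0.8. A 30% fall gave about 11%, 20-24% and 29%. (Log-SD 0.7 corresponds to CV √(e^0.49 − 1) = 0.80.) Categorical time did not help. Constrained randomisation lowered the worst case only from 29% to 25%. Moving the within-practice CV from 0.7 to 1.5 moved the case with a 20% fall and between-practice CV 0.5 from 17% to 8%. With no fall, or no spread between practices, the rate was 4-5%.

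**Step 4: direction.** Averaged over allocations, the bias is about 0.1% of the mean dose. Its SD over allocations is roughly 0.7-1.7% of the mean dose for 20-30% falls at CV 0.5-0.8. In the 29% case, 13.1 of the 28.9 points were false benefit.

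**Step 5: which feature causes it.** The set-up of step 2 was rerun with the same linear mg model but cluster-robust standard errors and t(21). It rejected in 4-7% of trials. Conversely, under an equal-mg fall (3-6 mg/day), a log-scale model with model-based standard errors rejected in 5-13% at log-SD 0.4 and 12-48% at 0.7. A repeat gave 6-53% overall. The linear model stayed at 5-6%.

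**Step 6: power for a proportional effect, no trend.** The relative efficiency of model (3) is about 1/(1 + CV²), where CV is between practices: 0.92, 0.80, 0.61 and 0.50 at CV 0.3, 0.5, 0.8 and 1.0. For a 5% reduction with within-practice CV 1.3:
- 114,000 patients, log-SD 0.7: 81-85% (linear) against 94-96% (log).
- 57,000, log-SD 0.7: 57% against 76%.
- 57,000, log-SD 0.4: 69% against 76%.

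**The case against.** The strongest reply is that the mg scale is not at fault. Step 5 bears this out: with cluster-robust standard errors the mg model holds its level, and a log link with model-based standard errors fails when the fall is a constant number of mg. Mg/day is also a legitimate estimand, given the concern in section 5.1 with excess opioid supply. A reader might infer that the identity scale alone invalidates the test, or that a log link is needed to repair it. Neither follows.

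The documents also do not describe a uniform percentage fall. Section 6 says only that prescribing is being constrained, without a figure or a pattern across practices. That practices differ widely in opioid level is plausible for these specialties, but it is not documented.

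On power, the loss is small or absent in some settings. A patient-level check with 15% zeros (57,000 patients, 150 trials, so imprecise) gave 67% against 68% at log-SD 0.4, though 41% against 62% at 0.7. At 114,000 patients and within-practice CV 1.0, both models reach 97-100% for effects of 5% or more.

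On importance, section 6 names opioid use at 3 months, which is closest to item 3d, and item 3c already uses a log link.

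All of this stands and limits the point. Three other provisions do not remove it. Section 12.5 mentions cluster-adjusted standard errors, but most naturally for t-tests and χ²-tests, with mixed models as a separate method. The moderator models of section 12.7.1 let the intervention effect vary by procedure, not the time trend. The procedure subgroups of section 12.6.1 might give each procedure its own time term, if they extend to 3a and 3b, but they leave the pooled test unchanged.

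**Conclusion.** The point holds conditionally. Items 3a and 3b rely on model-based standard errors from a model that cannot represent cluster-specific trends in mg. If use falls by 20-30% everywhere, with between-practice log-SD 0.4-0.7 and within-practice CV 1.3, type I error is about 6-14% at 57,000 patients and 7-23% at 114,000. It is higher if doses within a practice vary less. With a 10% fall or little spread between practices it is negligible. None of these inputs is in the documents.

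A reader might infer that the trial would tend to show a false reduction in opioid use. The calculations do not support that: false harm is about as likely as false benefit. The PROMIS primary analyses are not touched by this point. The power gain from a log link is real only for a roughly proportional effect and when practices differ widely.

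**What to change.** In section 12.5, items 3a and 3b:

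1. Base inference on cluster-robust standard errors with a small-sample correction for 22 clusters, whichever scale is used. Alternatives are a permutation test over the acceptable allocations of section 12.2.1 or a random cluster-by-period term.
2. Pre-specify a log-link mean model that allows zeros (for example quasi-Poisson or Tweedie), with the same cluster-robust inference. Report the ratio of means and the standardised mg/day difference.
3. State in advance which scale is the main one. This is a choice of estimand, and either can be defended.

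The cost is SAP wording, slightly wider intervals and some extra analysis; no data collection changes. The log link gains power only if the effect is roughly proportional. With model-based standard errors it would itself over-reject if the fall were a constant number of mg, so item 2 should not be adopted without item 1.
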